#### 10.4.1 Variable

The primary efficacy variable is the proportion of patients with NFPA reaching a tumor volume decrease of at least 20% after treatment Week 24 with pasireotide LAR.

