1.1.1 End-point for primary objective

Proportion of patients with NFPA who achieve tumor volume reduction of at least 20% after 24-week treatment with pasireotide LAR.

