Reduction of							
tumor							
volume ^{b)} , n (%)							
Yes							
No							
≥20% tumor							
volume							
reduction ^{c)} , n							
(%)							
Yes							
No			-		-		-
Total			-		-		-
≥20% tumor							
volume							
reduction using							
LOCF method, n							
(%)							
Yes			-		-		
No			-		-		
Total							

95%CI: 95% confidence interval.

a) The difference between visit i and V1.

b) For reduction='yes' will be considered all patients who obtained 'volume in visit i – volume in V1' >0.
c) For reduction ≥20%='yes' will be considered all patients who obtained 'Percentage change in volume at visit i' ≥20.

Table 8 – Time to response – FAS population

	Total		
	(n=xx)		
	Statistics	95% CI	
Time to response			
N			
Censored			
Events (Reduction ≥20% in tumor volume)			
Mean			
Median			
25 th Percentile			
75 th Percentile			
Range			

Cl_{95%}: 95% confidence interval.

Time between first administration and first date of reduction ≥20% in tumor volume.

Figure 3 – Kaplan-Meier curve for time to response – FAS population

Table 9 – Time to response versus baseline characteristics – FAS population

Time to response a)	Total					
	n=(xx) Statistics	Cl _{95%}	Statistics	Cl _{95%}		
	Statistics	C13576	Statistics	G19376		
Visual field at baseline	Normal		Abnormal			
Fime to response ^{a)}						
N						
Censored						
Events (progression or death)						
Mean						
Median						
25 th Percentile						
75 th Percentile						
Range						
Hazard ratio ^{b)}						
p-value						
Dose at V2	60 mg		40mg			
Time to response a)	oo mg		TVIIIS			
N						
Censored						
Events (progression or death)						
Mean						
Median						
25 th Percentile						
75 th Percentile						
Range						
Hazard ratio b)						
p-value						
•						
Dose reduction before response	Yes		No			
Time to response a)						
Time to response ^{a)} N Censored						
Time to response ^{a)} N						
Time to response ^{a)} N Censored Events (progression or death) Mean						
N Censored Events (progression or death) Mean Median						
N Censored Events (progression or death) Mean Median 25 th Percentile						
N Censored Events (progression or death) Mean Median 25 th Percentile 75 th Percentile						
N Censored Events (progression or death) Mean Median 25 th Percentile						
N Censored Events (progression or death) Mean Median 25 th Percentile 75 th Percentile						
N Censored Events (progression or death) Mean Median 25 th Percentile 75 th Percentile Range						

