n(%)	. ,									
Yes										
No										
Total										
Improved, n (%)										
Yes										
95%CI										
No										
Total										

Table 10 (Cont.) – Disease-related symptoms – FAS population

	Total (n=xx)									
	V1	V2	V3	V4	V5	V6	V7	V8	V9	V10
Regular menses ^{c)} ,	n									
(%)										
Yes										
No										
Total										
mproved, n (%)										
Yes										
95%CI										
No										
Total										

a) For each symptom, it will considered as improvement if the severity reduce at least one point (eg. 'Severe' at v₁ and 'moderate' at v₁ will be considered as improvement in vi).

b) For patients who registered 'No' in V₁ and 'Yes' in v_i it will be considered as an improvement in v_i.

c) For patients who registered 'No' in V₁ and 'Yes' in v_i it will be considered as an improvement in v_i.

Table 11 (Cont.) – Alpha-subunit – FAS population

	Total (n=xx)					
	V1	V4	V7	95%CI	V10	95%CI
α subunit (ng/mL)						
N				-		-
Mean				-		-
Median				-		-
Standard Deviation				-		-
Minimum				-		-
Maximum				-		-
Normal				-		-
Abnormal				-		-
CS				-		-
NCS				-		-
Reduction of α subunit ≥50% ^{c)} , n (%)						
Yes						
No						
Total						

CS: Clinically significant; NCS: Not clinically significant. 95%CI: 95% confidence interval.

c) For reduction ≥50%='yes' will be considered all patients who obtained percentage change from baseline in α subunit at visit i' ≥50.

Table 13 – Visual field – FAS population

	Total							
	(n=xx)							
	V1	V2	V4	V5	V7	V8	V9	V10
Right eye								
Normal/abnormal, n (%)								
Normal								
Abnormal								
Mild								
Severe								
Total								
Findings, n (%)								
Upper right quadrantanopia								
Upper left quadrantanopia								
Lower right quadrantanopia								
Lower left quadrantanopia								
Temporal hemianopsia								
Nasal hemianopsia								
Other								
Evolutive information, n (%)								
Stable								
Improved								
Worsened								
Total								
Left eye								
Normal/abnormal, n (%)								
Normal								
Abnormal								
Mild								
Severe								
Total								
Findings, n (%)								
Upper right quadrantanopia								
Upper left quadrantanopia								
Lower right quadrantanopia								
Lower left quadrantanopia								
Temporal hemianopsia								
Nasal hemianopsia								
Other								

Table 13 (Cont.) – Visual field – FAS population

	Total (n=xx)							
	V1	V2	V4	V5	V7	V8	V 9	V10
Left eye Evolutive information, n (%) Stable Improved Worsened Total								

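### The SAP's table footnotes reverse the sign of response: followed as written, tumours that grow by 20% or more count as responders and tumours that shrink do not

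*SAP*

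**What the plan says.** SAP 1.1.1 states the primary endpoint in the right direction: "Proportion of patients with NFPA who achieve tumor volume reduction of at least 20% after 24-week treatment with pasireotide LAR". Protocol 10.4.1 agrees: "The primary efficacy variable is the proportion of patients with NFPA reaching a tumor volume decrease of at least 20% after treatment Week 24". SAP 5.4.1 and 5.4.2 repeat this in words and give no formula.

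The coding rules are in the footnotes to the table shells in SAP Appendix 1. For Table 7 (MRI):

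- Footnote a, attached to both the volume-change row and the percentage-change row: "The difference between visit i and V1".
- Footnote b, for any reduction: "For reduction='yes' will be considered all patients who obtained 'volume in visit i – volume in V1' >0".
- Footnote c, for the primary responder row: "For reduction ≥20%='yes' will be considered all patients who obtained 'Percentage change in volume at visit i' ≥20".

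Table B 4 repeats all three for the extension visits. Table 11 uses the same form for alpha subunit, "For reduction ≥50%='yes' will be considered all patients who obtained percentage change from baseline in α subunit at visit i' ≥50", and Table B 6 repeats it. Table 10 gives identical wording to footnote b (erectile dysfunction) and footnote c (regular menses): "For patients who registered 'No' in V₁ and 'Yes' in v_i it will be considered as an improvement in v_i". Table B 5 lists the same two footnotes.

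**The concern.** A reduction makes visit i minus baseline negative. Footnotes b and c ask for a positive value, so they select increases. Footnote c defines the flag for the trial's single primary result, so a program that follows it would report the proportion of tumours that grew under the label of response.

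The result need not look wrong. In a proof-of-concept study with 19 evaluable patients and a 10% rate regarded as meaningful (SAP 5.6), one or two growing tumours would give a believable response rate. If the same flag is reused, the error reaches the LOCF sensitivity analysis, time to response, the Cox and logistic models, and the Table 6 row on dose reductions that came before response. In Table B 4, the row on maintained response among core-phase responders carries footnote c itself.

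Two secondary results are also affected. Rises in alpha subunit would count as reductions, and newly reported erectile dysfunction would count as symptom improvement.

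**Working it through.** **The plan's own figure.** With n = 19 and a true rate of 10%, P(X ≥ 2) = 1 - 0.9^19 - 19 × 0.1 × 0.9^18 = 1 - 0.1351 - 0.2852 = 0.580. This matches the 58% in SAP 5.6. The other entries of Table A 3 and the exact 90% intervals of Table A 4 also reproduce. The design figures are sound and do not depend on the sign rule.

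**The sign rule.** Let V1 be baseline volume and Vi the volume at visit i. Footnote b gives the difference as D = Vi - V1. The percentage change on the same scale is P = 100 × (Vi - V1)/V1. The endpoint requires P ≤ -20. Footnote b codes any reduction as D > 0, and footnote c codes response as P ≥ 20. With V1 = 10 cm³:

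| Vi | D | P (%) | Responder by SAP 1.1.1 | Footnote b: reduction | Footnote c: reduction ≥20% |
|---|---|---|---|---|---|
| 0 | -10 | -100 | yes | no | no |
| 5 | -5 | -50 | yes | no | no |
| 7 | -3 | -30 | yes | no | no |
| 8 | -2 | -20 | yes | no | no |
| 9.9 | -0.1 | -1 | no | no | no |
| 10.1 | +0.1 | +1 | no | yes | no |
| 12 | +2 | +20 | no | yes | yes |
| 13 | +3 | +30 | no | yes | yes |
| 15 | +5 | +50 | no | yes | yes |

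Since Vi ≥ 0, every shrinking tumour has P between -100 and 0 and can never satisfy P ≥ 20. Footnote c is therefore wrong for every patient whose change is 20% or more in either direction, and right only for those in between. Footnote b is wrong for every patient with a non-zero change.

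**Effect on the reported rate.** If r of n patients shrink by at least 20% and g grow by at least 20%, the correct rate is r/n and the coded rate is g/n. The error is (g - r)/n. The documents give no data, so the following split is assumed: n = 19, r = 4, g = 2 and 13 in between.

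- Correct rule: 4/19 = 21.1%, exact 90% CI 7.5% to 41.9%.
- Footnote c: 2/19 = 10.5%, exact 90% CI 1.9% to 29.6%. Both counted patients have growing tumours, and all 6 patients with a change of 20% or more are misclassified.
- If g = 0, footnote c gives 0/19 (exact 90% CI 0% to 14.6%) whatever the true response rate.

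**Alpha subunit.** With percentage change from baseline as 100 × (visit i - baseline)/baseline, a fall from 10 to 4 gives -60 and is coded no. A rise from 10 to 16 gives +60 and is coded yes.

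**Erectile dysfunction.** In Table 10, yes means the dysfunction is present. A move from no to yes is a new problem, yet footnote b scores it as improvement. The same wording is correct for regular menses, where yes is the desirable state.

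**The case against.** The strongest reply is that every narrative definition has the right direction, the row with footnote c is itself labelled as a reduction, and the documents show empty table shells rather than a program. A careful programmer might never follow the footnotes. That limits the claim to what would happen if the SAP were followed, but it does not remove the contradiction. The narrative gives no formula for the volume flag. SAP section 7 also requires any departure from the SAP's definitions to be accepted by the sponsor beforehand and documented, so quietly using the correct sign would be an unrecorded deviation on the primary endpoint. The clarifications listed in section 7 do not mention it.

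A narrower reply is that footnote a states no order of subtraction and footnote c gives no formula. If percentage change were computed as (V1 - Vi)/V1, footnote c would be correct. This is true of footnote c read alone. But footnote a governs the percentage-change row, and footnote b in the same table writes visit i minus V1. The SAP's other footnotes of this type (exposure in Table 6, disease duration in Table 3) only make sense as first-named minus second-named. No text records a decrease as positive. Footnote b is wrong on any reading.

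Three limits stand:

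- Only the continuation of Table 11 is in the available text, so a formula elsewhere in that table cannot be excluded. The alpha-subunit finding rests on the ordinary meaning of percentage change from baseline.
- The LOCF row, Table 6, Table 8 and the regression models carry no sign rule of their own. Table 8 names its event in the right direction. They inherit the error only if they reuse the flag.
- Erectile dysfunction is a separate coding error of the yes/no kind and adds no weight to the primary-endpoint point.

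**Conclusion.** The concern holds and must be fixed. As written, the SAP's derivation of the primary endpoint contradicts the endpoint. Among patients whose volume changes by 20% or more, misclassification is complete, and the reported rate is wrong by (g - r)/n, which is zero only when equal numbers shrink and grow. The same rule applies to the extension, including maintained response. The alpha-subunit flag is inverted on the ordinary reading, and the erectile-dysfunction rule is inverted outright.

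This rests on two assumptions: that the footnotes are followed, and that percentage change is taken in the order that footnote b writes out. The 4, 2 and 13 split is illustrative; the direction of the error does not depend on it.

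**What to change.** State the formulas once and use them throughout.

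- **Tables 7 and B 4, footnote a:** change = Vi - V1; percentage change = 100 × (Vi - V1)/V1.
- **Footnote b:** reduction is yes if Vi - V1 < 0.
- **Footnote c:** reduction of at least 20% is yes if percentage change ≤ -20.
- **Tables 11 and B 6:** reduction of at least 50% is yes if percentage change from baseline ≤ -50, with the same formula.
- **Tables 10 and B 5, footnote b (erectile dysfunction):** improvement is yes at V1 and no at visit i. Leave footnote c for regular menses as it is.
- **LOCF row, Tables 6, 8 and 9, and the regression models:** say that they use the corrected flag.

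Any program already written should be checked against two cases: V1 = 10 with Vi = 7 must return a responder, and V1 = 10 with Vi = 13 must not. The cost is SAP wording and that check. The sample size, data collection and trial conduct do not change.

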Symptom assessment/ Disease-related symptoms ⁴ (D)	х	х	Х	х	Х	х	Х	Х	х	х	Х	
ECOG performance status (D)	х	х	Х	х		х	Х	Х	х	х	Х	Х
ECG ¹⁴ (D)	х	х	Х	х		х	Х	х	х	Х	Х	
Serum pregnancy test 5,6	х							х			Х	
Hematology (BD)	х			х		х		х	х	х	Х	
Coagulation parameter PT (D)	х	Х	X ¹⁴	X ¹⁴	X ¹⁴	X ¹⁴	х				Х	
Coagulation parameter APTT (D)	х	Х					х				Х	
Urinalysis ⁶ (D)	х			x		х		х	x	х	Х	
Fasting Blood Glucose, Insulin ⁶	х			x		х		х	x	х	х	
HbA1c ⁶	х							х			Х	
Biochemistry ^{6,8} (D)	Х			х		х		х	Х	х	Х	
LFTs (ALT, AST, total bilirubin, albumin, ALP, γ-GT) (D)	х	х	X ¹⁴	X ¹⁴	X ¹⁴	X ¹⁴	Х				Х	
Hbs-Ag and anit-HCV (D)	Х											

Vitamin B12, folic acid ⁶	х										Х	
Hormonal evaluation ^{6,9} (D)	х			х				х			Х	
Alpha subunit evaluation ⁶	Х			х				Х			Х	
Visual field (camp) evaluation 10 (D)	х	X ¹⁰		х		х		х	x	х	Х	
Gallbladder ultrasound (D) 15	Х										Х	
Pituitary MRI / Sella turcica ¹⁵	Х			х				Х			Х	
Adverse events (D)		Х	Х	х	Х	х	Х	Х	х	х	Х	
Pasireotide LAR administration (D)		х		х		х		Х	x	х	X#	
Prior/Concomitant medications ¹¹ (D)	х	х	Х	х	Х	х	Х	Х	Х	х	Х	
Study completion ¹³ (D)												X ¹³

Pasireotide dose on this visit will be administered to selected patients, as per physician discretion, if the patient will be included in the Extension Phase based on response assessed by investigator/ benefit with the drug.

 $^{^{1}}$ Will be allowed a window of \pm 3 days for the planned visits and assessments, unless otherwise specified.

 $^{^{2}}$ It will be allowed a window of \pm 3 days for the planned visits and assessments, unless indicated otherwise.

³ To be completed prior to study drug administration

⁴ To be completed if the patient discontinues prematurely or at study completion.

⁵ Disease related symptoms that will be evaluated: headache, visual disturbances, fatigue, decreased libido, erectile dysfunction (for males only), irregular or stopped menses (for not post-menopausal female only). The investigator will also ask the patient to score the symptoms according to a five-point score scale (0=absent, 1=mild, 2=moderate, 3=severe, 4=very severe). The others will be assessed as present or absent.

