5.1 Populations for analysis

Full analysis set (FAS): consists of all patients who successfully completed the screening and have received at least one dose of study medication. FAS will be the primary set for all efficacy analyses.

Safety analysis set: consists of all patients who received at least one dose of study drug and had at least one post-baseline safety assessment.

Note the statement that a patient had no AEs (on the Adverse Event e-CRF) constitutes a safety assessment. The safety set will be used for all safety analyses.

The analyzes presented in this section represent the analyzes that will be used for the Core Phase of the trial. A final analysis will be performed when all patients of Extension Phase completed their last visit and will be reported or as additional clinical study report or as an addendum to the Core Phase of the trial report.

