5.5 SECONDARY OBJECTIVES

Population for the analysis

All secondary efficacy analyses will be based on the full analysis set (FAS). For all safety analyses, the safety analysis set will be used.

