5.5.1 Efficacy variables and analysis

The secondary efficacy endpoints are described in section 1.2.1.

The mean and percent change in tumor volume from baseline to Week 4, 12 and 24 will be presented along with the 90% confidence interval (CI). If data is found to be skewed, CIs for median will also be generated. Incidence rates for patients with \geq 20% reduction in tumor volume and its exact CI will be reported at Week 4 and 12.

Summary statistics will be provided for each disease related symptoms (headaches, visual disturbance, fatigue, symptoms specific to man and woman) at each visits. Change from baseline scores will be also summarized at each visit for all symptoms.

Time to response, defined as time from the first injection to first evaluation where patient achieve tumor volume reduction of at least \geq 20%, will be listed for all patients. If a patient has not achieved tumor response, the time of last assessment will be indicated as censoring time.

Kaplan-Meier analysis will be performed for time to response aiming to compute the median time to response and corresponding 95% confidence interval. Cox regression exploratory analysis will be used to estimate the hazard ratio with corresponding 95% confidence intervals for time to tumor volume reduction of at least \geq 20% as a function of baseline characteristics (duration of disease, dose at V2, dose reduction, visual field (abnormal/normal), and α subunit at V1).

Logistic regression will be performed to explore association between baseline characteristics and tumor response.

Frequency and percentage of patients who present improvement of symptoms related to tumor compression, pituitary hormonal dysfunction, alpha subunit level normalization, will be presented for each symptom at each time point with associated exact 95% CI.

Incidence rates of pituitary hormonal dysfunction, normalization of alpha subunit level and proportion of patients with 50% reduction in alpha subunit level along with its exact 95% CI will be reported at baseline, Week 4, 12 and 24. Analyses for alpha subunit level will be repeated with per protocol population set and for the subgroup of patients with elevated alpha subunit level at baseline.

Hormone profiles, alpha subunit levels and will be summarized at each time point in terms of frequency (N), mean, standard-deviation, median, minimum, and maximum.

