N Censored Events (progression or death) Mean Median 25 th Percentile 75 th Percentile Range Hazard ratio ^{b)} p-value						
N Censored Events (progression or death) Mean Median 25 th Percentile 75 th Percentile Range Hazard ratio ^{b)} p-value						
Time to response a) N Censored Events (progression or death) Mean Median 25 th Percentile 75 th Percentile Range Hazard ratio b) p-value Duration of disease (years)						
N Censored Events (progression or death) Mean Median 25 th Percentile 75 th Percentile Range Hazard ratio ^{b)} p-value Duration of disease (years) Hazard ratio ^{b)}						
N Censored Events (progression or death) Mean Median 25 th Percentile 75 th Percentile Range Hazard ratio ^{b)} p-value Duration of disease (years) Hazard ratio ^{b)}						
Time to response a) N Censored Events (progression or death) Mean Median 25 th Percentile 75 th Percentile Range Hazard ratio b) p-value Duration of disease (years) Hazard ratio b)						
Time to response a) N Censored Events (progression or death) Mean Median 25 th Percentile 75 th Percentile Range Hazard ratio b) p-value Duration of disease (years) Hazard ratio b) p-value						
Time to response a) N Censored Events (progression or death) Mean Median 25 th Percentile 75 th Percentile Range Hazard ratio b) p-value Duration of disease (years) Hazard ratio b)						

Cl_{95%}: 95% confidence interval.

Time between first administration and first date of reduction ≥20% in tumor volume.

a) Kaplan-Meier estimates. b) Cox regression estimates.

Table 10 – Disease-related symptoms – FAS population

	Total									
	(n=xx) V1	V2	V3	V4	V5	V6	V7	V8	V9	V10
Headache ^{a)} , n (%)										
Absent										
Mild										
Moderate										
Severe										
Very severe										
Total										
Improved, n (%)										
Yes										
95%CI										
No										
Total										
Visual disturbances a),	n									
(%)										
Absent										
Mild										
Moderate										
Severe										
Very severe										
Total										
Total										
Improved, n (%)										
Yes										
95%CI										
No										
Total										

Table 10 (Cont.) – Disease-related symptoms – FAS population

	Total									
	(n=xx)									
	V1	V2	V3	V4	V5	V6	V7	V8	V9	V10
Fatigue ^{a)} , n (%)										
Absent										
Mild										
Moderate										
Severe										
Very severe										
Total										
Improved, n (%)										
Yes										
95%CI										
No										
Total										
Erectile dysfunction	1 b)									

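### Headache, visual disturbances and fatigue: the denominator of the improvement percentage is not stated and is not limited to patients who had the symptom at V1

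*SAP*

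**What the plan says.** SAP section 5.5.1 plans "Frequency and percentage of patients who present improvement of symptoms related to tumor compression" and says that these "will be presented for each symptom at each time point with associated exact 95% CI". It names no denominator.

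SAP section 5.5 places all secondary efficacy analyses on the FAS, which "consists of all patients who successfully completed the screening and have received at least one dose of study medication" (SAP section 5.1). Membership does not depend on having any symptom. The core-phase table is headed "Table 10 – Disease-related symptoms – FAS population", and each *Improved* block has rows for *Yes*, the 95% CI, *No* and *Total*. Table B 5 repeats the *Improved* rows for the extension, without CI rows and without a V1 column.

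Footnote a to both tables sets the rule for graded symptoms: "it will considered as improvement if the severity reduce at least one point". The scale, given in the footnotes to SAP Table A 1, is "0=absent, 1=mild, 2=moderate, 3=severe, 4=very severe". The symptoms shown in Table 10 on this scale are headache, visual disturbances and fatigue.

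Erectile dysfunction and regular menses are recorded as *Yes* or *No*. Footnotes b and c both count a move from *No* at V1 to *Yes* later as improvement.

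For alpha subunit, section 5.5.1 repeats the analysis "for the subgroup of patients with elevated alpha subunit level at baseline". It plans no counterpart for symptoms.

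**The concern.** A patient without headache at V1 cannot fall a point on the headache scale. If that patient stays in the denominator, the only row available is *No*. The percentage improved then mixes two things: how often the symptom improves under treatment, and how many patients had it at entry. The second will differ from symptom to symptom, so the percentages cannot be compared down the table. The exact CI is attached to the mixed quantity.

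Patients without a given symptom are to be expected. No inclusion criterion requires one (SAP section 3.1.1). Exclusion criteria 1 and 6 remove patients who need surgery for compression signs or symptoms, and those with acute, clinically significant visual field defects from chiasm compression. Protocol Table 1-1 describes these adenomas as mostly without symptoms.

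The effect on disease-related symptoms is a stated secondary objective, so a reader will look to these rows for an answer.

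**Working it through.** **Method check.** The plan states no figure for symptom improvement. Its own binomial figures can be reproduced with the exact (Clopper-Pearson) method used below. For 2 to 6 responders of 19, the 90% limits come out as 1.9–29.6, 4.4–35.9, 7.5–41.9, 11.0–47.6 and 14.7–53.0%, matching SAP Table A 4. The probability of at least 2 responders of 19 at a true rate of 10% comes out as 58.0%, matching the stated 58%.

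**Inputs.** N = 23 is the planned enrolment (SAP section 5.6). The interval is exact 95% (SAP section 5.5.1 and the Table 10 rows). The number with the symptom at V1, m, is not in the documents; I assume 6, 12, 17 and 23. I also assume that half of the symptomatic patients improve, or just under half when m is odd.

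**Formula.** Let x be the number improved. Because only the m symptomatic patients can improve,

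x/N = (x/m) × (m/N).

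The FAS rate is therefore the rate among symptomatic patients scaled by m/N, and m/N is also the highest value it can reach. For m = 12: 6/12 × 12/23 = 0.500 × 0.522 = 26.1%.

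| m of 23 | Improved x | FAS rate x/23 (95% CI) | Rate among symptomatic x/m (95% CI) | Ceiling m/23 |
|---|---|---|---|---|
| 6 | 3 | 13.0% (2.8–33.6) | 50.0% (11.8–88.2) | 26.1% |
| 12 | 6 | 26.1% (10.2–48.4) | 50.0% (21.1–78.9) | 52.2% |
| 17 | 8 | 34.8% (16.4–57.3) | 47.1% (23.0–72.2) | 73.9% |
| 23 | 11 | 47.8% (26.8–69.4) | 47.8% (26.8–69.4) | 100% |

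For m = 6 and m = 12 the FAS interval does not contain the 50% rate among symptomatic patients.

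**Observed cases.** SAP section 5.4.3, written under the primary objective, says that all analysis uses observed data. If that governs here, N and m are counted among patients with values at V1 and at the visit, and the formula is unchanged. With N = 19 (the planned evaluable number) and m = 6, 12 and 17, the rates over all patients are 3/19 = 15.8%, 6/19 = 31.6% and 8/19 = 42.1%.

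**The two yes/no symptoms.** Taking footnotes b and c literally:

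- Regular menses: *No* to *Yes* is a gain. The patients who cannot improve are women with *Yes* at V1.
- Erectile dysfunction: *No* to *Yes* is new dysfunction, so only men without the symptom at V1 can be counted as improved. This is a separate error of direction. Limiting this row to men with dysfunction at V1 while footnote b stands would force the numerator to zero.

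**The case against.** The best counter-argument is that the denominator is undefined rather than wrong. In this SAP the FAS label names the source population and does not always fix the base of each row. Table 14 carries it above rows conditional on the scan having been done. Table B 4 carries it above rows limited to core-phase responders. Table 10 itself carries it above symptoms assessed only in men or only in women who are not post-menopausal. That stands: a reader might infer that the SAP prescribes the whole FAS as denominator, but no sentence or footnote says so. FAS, perhaps limited to observed cases, is only the default reading. The adverse event tables do state their bases; the symptom tables do not.

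A second tempting inference is that the symptom results are biased toward no effect. That goes too far. The share of all treated patients who improve is a legitimate quantity, but it answers a different question. The trial is single-arm with no test planned on symptoms, and the listed endpoint is change in score, which is summarised separately.

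Third, Table 10 prints the V1 severity counts, so a reader can see how many patients scored 0. This helps in part. With complete data the point estimate can be rebuilt, but the printed CI keeps the wider base. With missing visits the V1 counts do not give the number symptomatic among those seen. Table B 5 has no V1 column, and extension entry is at the treating physician's discretion, so Table 10's V1 counts do not describe those patients.

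Finally, the alpha-subunit precedent repeats the analysis in a subgroup and does not replace the main one. That is a fair point, and it is why the FAS figure may stay as a supplement.

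**Conclusion.** The point holds for headache, visual disturbances and fatigue in Tables 10 and B 5. The denominator is not stated, and nothing limits it to patients who could improve. On the default reading, dilution occurs whenever any patient in the denominator scores 0 at V1, by the factor m/N.

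Its size cannot be determined from the documents. Over the assumed range it runs from none (m = 23) to a reported 13.0% in place of 50% (m = 6). These are illustrations and not forecasts. The nearest documentary figure is the 60% to 80% of patients with visual field defects in protocol section 1.1 (0.6 × 23 = 13.8 to 0.8 × 23 = 18.4 patients). That is a perimetry finding in patients with these adenomas generally, not the graded symptom score in a population from which some such patients are excluded.

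A reader might extend the same mechanism to every symptom row. The documents do not support that for erectile dysfunction, where footnote b runs the other way. The CI argument applies only to Table 10, because Table B 5 has no CI rows.

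The consequence is limited to a descriptive secondary summary in a single-arm proof-of-concept study. The primary endpoint is untouched. Because the correction is so cheap, it should still be made.

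**What to change.** Amend the footnotes to Tables 10 and B 5:

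- **Headache, visual disturbances, fatigue:** compute the percentage improved among patients with a score of at least 1 at V1 and a value at the visit in question. Show that n at every visit. In Table 10, base the exact 95% CI on it.
- **New onset:** report separately, among patients scored 0 at V1 with a value at the visit, how many developed the symptom.
- **Regular menses:** use women who are not post-menopausal and have *No* at V1.
- **Erectile dysfunction:** first correct footnote b so that *Yes* to *No* counts as improvement, then use men with the symptom at V1.
- **FAS percentage:** keep it as a supplement if wanted, labelled as the share of all treated patients.

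The cost is a few lines of footnote and table programming, with no new data. The denominators become smaller and the intervals wider: for m = 12 in the illustration, 21.1–78.9% instead of 10.2–48.4%.
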